Version: 2.0 Date: 24APR2017

A Randomized, Double-Blind, Vehicle-Controlled, Parallel, Phase II Study to Evaluate Efficacy and Safety of BAC in Patient with Alzheimer's Disease or Vascular Dementia

NCT Number	NCT02886494
Document Version	V2.0
Document Date	24APR2017
Sponsor	Charsire Biotechnology Corp.

PROTOCOL SUMMARY

Version: 2.0

PROTOCOL SUMMARY
A Randomized, Double-Blind, Vehicle-Controlled, Parallel, Phase II Study to Evaluate Efficacy and Safety of BAC in Patient with Alzheimer's Disease or Vascular Dementia
BAC for Alzheimer's Disease or Vascular Dementia Phase II Study
BAC-02
Phase II
Charsire Biotechnology Corp.
To evaluate the efficacy and safety of BAC in patients with Alzheimer's disease or vascular dementia
Randomized, double-blind, vehicle-controlled, parallel study
Patient aged at least 40 years old in United States diagnosed with Alzheimer's disease or vascular dementia
The sample size is determined to be 45 versus 15 patients (3:1 ratio) for Treatment versus Control groups, 60 patients in total. To ensure the completion of 60 evaluable (per-protocol population) patients, around 75 patients will be recruited.
BAC (vapor fraction from seeds of Glycine max (L.) Merr . and composition thereof), topical application on external nasal skin, scalp, and neck, 2 times daily, 30g/day
During the treatment period, patients may continue to receive routinely used medications or treatments for Alzheimer's disease or vascular dementia.
Twelve weeks
Screening, Randomization (Baseline) Treatment (Weeks 2, 4, and 8 compared to Baseline), Final (Week 12)
In each study site, patients who meet all eligible requirements for entry into the study will be randomized and stratified into 1 of 2 dementia types (Alzheimer's disease and non- Alzheimer's disease) into treatment group or vehicle control group in 3:1 ratio as shown below:

Treatment Group:

BAC

Control Group:

Matched vehicle

Note: Dementia types (Alzheimer's disease and non- Alzheimer's disease) are classified as follows:

- 1. Alzheimer's disease: Alzheimer's disease according to the NIAAA criteria + "Mixed" dementia (possible Alzheimer's disease with cerebrovascular disease) according to the NIAAA criteria
- Non- Alzheimer's disease: Vascular dementia according to the NINDS-AIREN International Workshop criteria

Patients Inclusion Criteria

A patient is eligible for the study if all of the following apply:

- 1. With either gender aged at least 40 years old

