16. Caregivers who have psychotic symptoms, are imminently suicidal, have an unstable medical condition (e.g. recent heart attack, recent stroke, episodes of dizziness, fainting attacks) or significant orthopaedic problems.

Primary Endpoint

Efficacy:

Change in Alzheimer Disease Assessment Scale-cognitive (ADAScog) score at Week 12 visit compared to baseline

Secondary Endpoints

Efficacy:

- 1. Change in ADAS-cog score at all post treatment visits (except Week 12 visit) compared to baseline
- Clinician's Interview Based Impression of Change-Plus
 Caregiver Input (CIBIC-plus) score at all post treatment visits
- 3. Change in Alzheimer's Disease Cooperative Study Activities of Daily Living (ADCS-ADL) score at all post treatment visits compared to baseline
- 4. Change in MMSE score at all post treatment visits compared to baseline
- 5. Change in Neuropsychiatric Inventory (NPI) score at all post treatment visits compared to baseline

Safety:

- 1. Adverse event incidence
- 2. Change in physical examination results
- 3. Net change from baseline in laboratory test results
- 4. Net change from baseline in vital signs

Statistical Analysis

Analysis Population

Two data sets will be introduced for statistical analysis.

Intent-to-treat (ITT) population:

 All randomized patients who have received at least one dose study medication.

Per-protocol (PP) population:

Sponsor: Charsire Biotechnology Corp.

Version: 2.0

(Project Number: BAC-02) Date: 24APR2017

Version: 2.0

- A subset of ITT population
- Fulfill all inclusion and exclusion criteria
- Accumulatively dosed with at least 63 days of study drug and with at least 75% of dosing compliance during treatment period
- With ADAS-cog score evaluation at or after Week 8 visit
- Did not receive any prohibited treatment during the study

Efficacy endpoints will be analyzed on ITT and PP population. Demographics, baseline characteristics, and safety endpoints will be analyzed on ITT population. The conclusion of efficacy will be made according to the results of ITT population analysis.

Analyses

Demographics and baseline characteristics will be summarized for each group by using descriptive statistics.

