The efficacy endpoints will be compared between the BAC group and vehicle group. The primary endpoint of this study is change in ADAS-cog score at Week 12 visit compared to baseline. The test will be performed by ANCOVA with treatment group and center as factor and with baseline score as covariate. Test treatment group will be declared superiority if the null hypothesis is rejected and improvement in ADAS-cog of test product group is greater than that of matched vehicle group.

As for secondary endpoints, change in ADAS-cog score at all post-treatment visits (except Week 12 visit) compared to baseline will be analyzed by ANCOVA with treatment group and center as factor and with baseline score as covariate. Same statistical analysis methods will be applied for other secondary endpoints such as changes in ADCS-ADL score, MMSE score, and NPI score at all post treatment visits compared to baseline. The CIBIC-plus score at all post treatment visits will be presented by transition table.

All treatment group comparisons will be conducted with significance level of 0.05, using 2-tailed tests.

For safety analyses, adverse events will be reported by treatment groups and by physiological systems as appropriate. Incidence of adverse events between treatments will be analyzed by CMH test.

Changes in physical examinations will be displayed for each individual system. Net changes from pre-treatment laboratory test results and vital signs will be analyzed by descriptive statistics.

All treatment group comparisons will be conducted with significance level of 0.05, using 2-tailed tests.

Additionally, descriptive statistics will be provided for all of the endpoints. Frequency table will be provided for categorical data, while mean, standard deviation, maximum, minimum, median, interquartile range (IQR), and 95% two-sided confidence interval will be calculated for continuous measurements.

Version: 2.0

SCHEDULE OF ASSESSMENTS

Visit	Screening	Randomization ¹ (Baseline)	Treatment		Final	
Visit No.	1	2	3	4	5	6
Weeks relative to Baseline visit	-2~0	0	2	4	8	12
Visit Window (days)	NA	NA	±4	±4	±4	±4
Informed consent signed and given	X					
Screening number assignment	X					
Randomization		X				
Demographic data & medical history	X					
Inclusion and exclusion criteria	X	X				
Pregnancy test for applicable patients	X					
Imaging (CT/MRI)	X ⁵					
ADAS-cog	X	X		X	X	X
CIBIS/CIBIC-plus ²		X		X	X	X
ADCS-ADL		X		X	X	X
MMSE	X	X		X	X	X
NPI		X		X	X	X
Vital signs	X	X	X	X	X	X

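### Randomization is stratified by dementia type, but the ANCOVAs leave dementia type out, which forgoes power if it predicts 12-week change

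*Combined protocol and SAP*

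**What the plan says.** The Protocol Summary describes 3:1 randomization as carried out separately at every site and by dementia type. Eligible patients "will be randomized and stratified into 1 of 2 dementia types". Its note defines two types. One is Alzheimer's disease with mixed dementia included; the other is vascular dementia. The randomization strata are therefore site by dementia type.

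Under Statistical Analysis, Analyses, the primary model for Week 12 change in ADAS-cog is given as: "The test will be performed by ANCOVA with treatment group and center as factor and with baseline score as covariate". The ADAS-cog changes at the other visits get the same terms. For the remaining scales the plan says: "Same statistical analysis methods will be applied for other secondary endpoints such as changes in ADCS-ADL score, MMSE score, and NPI score". CIBIC-plus is not modelled: "The CIBIC-plus score at all post treatment visits will be presented by transition table".

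None of these analyses contains dementia type. The documents give no reason for leaving it out, and no sensitivity or subgroup analysis uses it.

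**The concern.** Stratified allocation makes the arms nearly balanced on dementia type, so little of any outcome difference between the types can enter the treatment contrast. A model without the factor still leaves that difference in the residual. The reported standard error is then larger than the true sampling variation of the treatment estimate. The test rejects too seldom under the null and loses power under the alternative.

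The comparison is planned around 45 versus 15 evaluable patients. At 3:1, 75 recruits would still give only about 75/4 ≈ 19 on vehicle, so precision is scarce. The sponsor also chose this factor as the one worth balancing. If dementia type does not predict change, nothing is lost.

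**Working it through.** **Inputs from the documents.** 3:1 allocation, 45 versus 15 (60 evaluable); "around 75 patients will be recruited"; two-sided 0.05; ANCOVA terms as above; strata of site by dementia type.

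**The plan's own figure.** No effect size, SD or target power is given, so 45 versus 15 cannot be reproduced. Working backwards, SE = √(1/45 + 1/15) = 0.298 SD units, so 80% power needs (1.960 + 0.842) × 0.298 = 0.835 SD. The recruitment figure agrees with 20% non-evaluable: 60/(1 − 0.20) = 75.

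**Assumptions, not in the documents.** Treatment effect 0.85 SD; share with Alzheimer's disease p = 0.70; permuted blocks of 4 within center by type; 1, 3 or 10 centers; within-type residual SD 1; baseline coefficient 0.3, with baseline independent of type. The difference in mean change between types, after baseline and center, is g SD.

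**Hand calculation** (perfect balance, normal approximation). With type omitted, the residual variance is 1 + g²p(1 − p), while the true SE of the contrast stays at 0.298. Let k be the square root of that variance. The effective critical value is 1.96k, and power is Φ(0.85/0.298 − 1.96k) = Φ(2.851 − 1.96k). With type included, power is Φ(2.851 − 1.96) = 81.4%.

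- g = 0.5: variance 1 + 0.25 × 0.21 = 1.0525; k = 1.026; critical value 2.011; type I error 0.044; power 80.0%. Loss about 1.4 points.
- g = 1.0: variance 1 + 0.21 = 1.21; k = 1.10; critical value 2.156; type I error 0.031; power 75.7%. Loss about 5.7 points.

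**Simulation** (20,000 trials per setting, incomplete blocks allowed; Monte Carlo SE about 0.3 power points). Power with type omitted vs included, N = 60:

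| g | 1 center | 3 centers | 10 centers |
|---|---|---|---|
| 0 | 78.6 vs 78.6% | 79.0 vs 78.8% | 77.1 vs 76.6% |
| 0.25 | 79.2 vs 79.4% | 78.4 vs 78.7% | 76.5 vs 76.4% |
| 0.5 | 77.7 vs 79.4% | 77.5 vs 78.9% | 75.6 vs 76.7% |
| 1.0 | 72.8 vs 79.0% | 72.7 vs 79.1% | 70.5 vs 76.9% |

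At g = 0.75 the gap is about 3 to 4 points. At g = 1.0 with type omitted, type I error is 0.033 / 0.037 / 0.039 for 1 / 3 / 10 centers. The mean model SE against the empirical SD of the estimate is 0.330 vs 0.303, 0.331 vs 0.307 and 0.339 vs 0.323, so it is 9%, 8% and 5% too large. With type included, the two agree within 0.003.

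**Sensitivity.**

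- N = 75: about 1 point at g = 0.5. At g = 1.0, 83.1 vs 87.7%, 82.8 vs 87.7% and 81.0 vs 86.1%, a gap of 4.6 to 5.1 points.
- 85% Alzheimer's disease, N = 60: under 1 point at g = 0.5 and 3.4 to 3.9 points at g = 1.0.
- 50% Alzheimer's disease, N = 60 (effect 0.835 SD, baseline coefficient 0.5, 3,000 trials per setting): at g = 1.0, 68.2 vs 76.8% with 1 site, 68.7 vs 77.1% with 5 and 65.8 vs 75.2% with 10, a gap of 8 to 9 points.
- Total SD, not within-type SD, held at 1: power of the planned model does not fall, but the adjusted model gains 6 to 7 points over it at g = 1.0 and 1 to 2 points at g = 0.5.

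**The case against.** The strongest objection is that nothing in the documents shows dementia type to be prognostic. The larger losses need a 1.0 SD difference between types after adjustment, which exceeds the assumed treatment effect. Mixed dementia is pooled with Alzheimer's disease, all types share the same MMSE and ADAS-cog entry limits, and baseline score and center are already in the model. All of this could narrow the contrast. This stands as a limit on size: the upper end is a possibility and not an expectation.

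The analysis set also matters. The plan says: "The conclusion of efficacy will be made according to the results of ITT population analysis". Sixty is the per-protocol target, so N = 60 is the unfavourable end of a range that reaches 75. Both ends are shown above.

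Two qualifications concern type I error. The conservatism depends on restricted allocation within strata, and the documents give no block size or method. With unrestricted allocation, simulated type I error for the planned model at g = 1.0 was 0.050 to 0.056, so not conservative. Separately, if vehicle-arm SD were 1.3 or 1.5 times that of the treated arm, the 3:1 ratio would raise type I error to about 0.08 or 0.10 in the planned model, and the adjusted model is affected too. That is a different issue, and it does not bear on whether the stratification factor belongs in the model.

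Finally, the available text is a summary, so a fuller section could hold a subgroup or sensitivity analysis. The model wording is nevertheless complete and is stated for both the primary endpoint and the secondary ADAS-cog visits.

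**Conclusion.** The concern holds. The design stratifies on dementia type and the ANCOVAs ignore it. Under blocked allocation and equal variances, the omission makes the test conservative when dementia type is prognostic. It adds no inflation of type I error, and the planned test remains valid.

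Under the stated assumptions the power forgone runs from nil (difference of 0.25 SD or less), through 1 to 2 points (0.5 SD), to roughly 5 to 7 points (1.0 SD, N from 75 down to 60, 70% Alzheimer's disease). It is smaller if one type dominates and larger if the types are evenly split. The mismatch itself is certain; the size of the loss cannot be fixed from the documents. The change should be made because it is nearly free, not because the trial fails without it.

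**What to change.** Before unblinding, add dementia type (two levels, as randomized) as a factor alongside treatment, center and baseline score. Apply this to Week 12 change in ADAS-cog and to the secondary ANCOVAs of ADAS-cog, ADCS-ADL, MMSE and NPI change. Leave the CIBIC-plus transition table as it is. Adding the term after unblinding would look data-driven.

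The cost is one sentence of analysis text and one degree of freedom. No new data are needed, because the stratum is recorded at randomization. If dementia type turns out not to be prognostic, the simulated power cost is 0 to 0.2 points with 1 or 3 centers and 0.5 to 0.8 points with 10.
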